4.4 Duration of Treatment

Patient can continue study treatment at the treating physician's discretion. Patients achieving at least a stable disease can continue treatment until one of the following is reached:

- Progression of disease
- Death
- Unacceptable toxicity
- Patient decision
- Treatment delay greater than 4 weeks.

Overall response will be assessed after 4, 8, and 12 cycles. If disease progression is observed at the end of Cycle 4 evaluation, all study therapy will be discontinued. In addition, study therapy will be discontinued at the time of disease progression as noted above. Otherwise patient can continue treatment until one of the above endpoints is reached.

Following the 30-day post-treatment follow-up assessment, additional evaluations will occur once per month (unless subject discontinued due to progression) until the earliest of the following events:

- Disease progression,
- The time of initiation of new therapy,
- Death or study completion.

Study completion is defined as 30 days after the last subject remaining on study medication discontinues study medication.

4.5 Study Accrual

For the phase I portion, a minimum of 12 and a maximum of 30 patients will be recruited. Once the MTD has been established, an additional 23 subjects will be treated at the MTD in the phase II.

4.6 Duration of Study Period

The total study enrollment period is expected to be up to 24 months.

5 TREATMENT PLAN AND PROCEDURES

For the Phase I portion, this is a standard 3+3 design over 4 dose levels of 1.5, 3, 3, and 6 mg/kg of CT-011 given intravenously every 4 weeks (every 28 days) on day 3, and lenalidomide given at 15, 15, 25, and 25 mg orally daily on days 1-21 of a 28-day cycle. The study drug CT-011 and lenalidomide can be escalated or de-escalated independently of one another as described in the Table below. Twelve to 30 patients will be recruited in the phase I portion of the trial. The phase II portion will utilize the 6 patients treated at the MTD in the phase I portion and an additional 23 patients will be accrued. Dexamethasone 40 mg orally weekly may be added if only stable disease after 3 cycles according to the IMWG response criteria (section 13-0). Dexamethasone can be reduced to 20 mg based on tolerability or if patient is 70 years or older.

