- If ≥ 2 patients in cohort 4 exhibit a DLT at the dose of 6 mg/kg CT-011 in combination with lenalidomide 25 mg, 3 more patients will be enrolled at the 6 mg dose of CT-011 in combination with 15 mg lenalidomide. If there is < 1 DLT with CT011 6mg/kg and lenalidomide 15 mg, this will be defined as the MTD. If there are 2 or more DLT, then 3 additional patients will be enrolled at the CT-011 6mg/kg and lenalidomide 10 mg, which will become the MTD

To determine dose escalation, we will focus on the number of patients who experience dose limiting toxicity; i.e. a patient who experiences more than one DLT will be counted only once.

Discontinuation of treatment due to disease progression will not constitute a DLT.

In the Phase 1 portion of the study, subjects who withdraw or prematurely discontinue treatment before completing the first treatment cycle for reasons other than toxicity and DLT will be replaced.

After 4 cycles of therapy or earlier if clinically indicated, response determination will be assessed by the IMWG criteria. At the end of Cycle 4, if a subject has responded (complete or partial response) or has stable disease, dosing with CT-011, lenalidomide and dexamethasone(if initiated after cycle 1-2) will continue for a minimum of 8 additional cycles or until withdrawal.

For the Phase II portion

Upon determination of the MTD in the phase I portion of this trial, the phase II portion of the study will commence enrollment at the MTD determined in the phase I portion with CT-011 in combination with lenalidomide. In the event that a MTD is not established, safety and tolerability data collected in the Phase I portion of the study will guide decisions on dosing of CT-011 in the phase II trial.

Dexamethasone 40 mg orally weekly may be added if only stable disease after 3 cycles according to the IMWG criteria (section13). Dexamethasone can be reduced to 20 mg based on tolerability or if patient is 70 years or older.

During the phase II portion of this trial, we will not evaluate patients for DLTs as was done in the phase I portion; however, we will use the DLT criteria to identify potential toxicity and tolerability concerns occurring at any cycle to initiate further evaluation to ensure safety of patients. An independent Data and Safety Monitoring Committee will continue oversight of this trial. See Appendix E for details.

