5.7 Patient Withdrawal

A patient should be removed from the study whenever it is necessary to safeguard his/her welfare. Occurrence of a significant adverse event or laboratory abnormalities unexpected for these patients may also necessitate discontinuation from the study. Additional reasons for removing a patient from the study are:

- Patients who participate in another investigational drug trial
- Patients' non-compliance with the protocol that can negatively affect the treatment effect
- Patients who express a desire to withdraw from the study (the patient has the right to withdraw for any reason without prejudice)
- Evidence of progressive disease would require withdrawal of the patient from the study.
- Any other reasons deemed by the principal investigator and treating physician.
- Patients who must discontinue use of either CT-011 or lenalidomide

The reason for any patient withdrawal from the study should be recorded on the case report form (CRF) and the occurrence should be reported to the principal investigator by email. These patients who withdraw from the study in the phase II portion of the trial will not be replaced. When a patient is removed from the study, he/she will receive treatment according to the standard of care (SOC) in the medical center and will be followed-up according to the study schedule whenever possible.

A patient who is removed from the study by the investigator due to an adverse event (AE) or serious adverse event (SAE) will be followed until resolution of the toxicity to Grade 1 or baseline. All the tests that are required to assess the patient condition will be made as frequent as necessary until the AE or SAE has been resolved. Samples that have already been obtained will be processed.

A patient who withdraws consent before starting the study will not be followed up.

A patient who is removed from the study by the investigator since he/she did not keep the appointments will be hard to follow given the circumstances. The extreme situation of this occurrence is a patient who is defined as "lost to follow-up". Attempts to follow up on the subject will be made as long as the consent has not been withdrawn by the subject. Samples that have already been obtained will be processed.

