Previous studies of lenalidomide alone in a similarly defined relapsed/refractory MM patient population has shown an overall response rate of 25%, which also included the addition of dexamethasone after 2 cycles to non-responding stable disease patients. We will consider this regimen promising if the true overall response rate is 50% or greater when lenalidomide is combined upfront with CT-011. Therefore, we will test the null hypothesis that the true overall response rate (ORR) is at most 25% (reflecting a combination regimen ORR that would not be of interest) versus our alternative hypothesis that the true ORR in patients treated with this combination regimen is at least 50%.

Decision Rule: The largest response rate where this treatment regimen would be considered ineffective in this population is 25%, and the smallest response rate that would warrant subsequent studies with this proposed regimen in this patient population is 50%. The following Three-Outcome phase II study design is a modification of the standard one-stage phase II design and uses a maximum of 29 evaluable patients to test the null hypothesis that the true response rate is at most 25%. Since we will include the 6 patients treated at the MTD from the phase I portion of the trial, this will require accruing an additional 23 evaluable patients for this phase of the study. Based on this study design, there are three possible outcomes:

- **Not promising**: This regimen will be classified as not promising with respect to the response rate in this patient population if at most 9 patients have any response after 4 cycles of therapy out of the total 29 evaluable patients.
- **Promising**: This regimen will be classified as promising with respect to increasing the response rate in this patient population if at least 12 patients have an observed response to treatment after 4 cycles of therapy out of the total 29 evaluable patients. Subsequent larger confirmatory studies may be warranted.

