10.7 Patient Withdrawal and Study Termination

A patient should be withdrawn from the trial treatment if, in the opinion of the investigator, it is medically necessary, or if it is the wish of the patient. If a patient does not return for a scheduled visit, every effort should be made to contact the patient. In any circumstance, every effort should be made to document patient outcome, if possible.

Patients should be removed from therapy if any of the following occurs:

- The occurrence of unacceptable toxicity indicating the need for cessation of treatment. Patients may continue with correlative studies.
- Patient has progressive disease while receiving treatment
- The physician feels it is in the best interest of the patient to stop treatment and the physician may determine whether to continue with correlative studies.
- Patient refusal to continue with therapy.
- Non-compliance by the patient with protocol requirements.
- Patient is lost to follow-up. If a patient does not return for scheduled visits, every effort should be made to re-establish contact. In any circumstance, every effort should be made to document patient outcome, if possible.
- Patient becomes pregnant.
- Termination of the study.

If a patient withdraws from protocol therapy, it should be clearly documented with additional notation of whether the patient has agreed to complete follow up as outlined in the protocol. Subsite

institutions must notify the OSU Subsite Coordinator as soon as possible if the patient withdraws from protocol therapy and must provide the documentation of the reason and whether the patient will complete follow up.

The reason and date of discontinuation are to be documented in the patient's medical record and in the CRF.

The investigator should complete all end of treatment procedures when a patient withdraws from treatment. All patients who discontinue the trial secondary to an adverse event should be followed until resolution, stabilization or return to a baseline condition.

Patients who fail to complete treatment for reasons other than adverse event or unacceptable toxicity may be replaced. All patients who receive one dose of study treatment should be included in any safety analysis.

The investigator may discontinue the trial at any time. Reasons for early trial discontinuation may include, but are not limited to, unacceptable toxicity of study treatment, a request to discontinue the trial from a regulatory authority or an IRB, or poor enrollment.

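### The plan does not settle whether phase I patients replaced in cycle 1 count in the pooled response rate, and its replacement and denominator rules conflict, so the 4% type I error is not assured

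*Combined protocol and SAP*

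**What the plan says.** **Pooling.** Section 5: "The phase II portion will utilize the 6 patients treated at the MTD in the phase I portion". Section 6.1.2 repeats it ("Since we will include the 6 patients treated at the MTD from the phase I portion of the trial") and adds 23 new evaluable patients to reach 29.

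**Decision rule (6.1.2).** The plan says "we will test the null hypothesis that the true overall response rate (ORR) is at most 25" percent, and that "the smallest response rate that would warrant subsequent studies with this proposed regimen in this patient population is 50" percent. At most 9 responders after 4 cycles is not promising, 10 or 11 is inconclusive, and 12 or more is promising. The stated type I and type II errors are 4% and 3%, with eta 0.83 and pi 0.87.

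**Replacement in phase I.** Section 4.3: "subjects who withdraw or prematurely discontinue treatment before completing the first treatment cycle for reasons other than toxicity and DLT will be replaced". It also says: "Discontinuation of treatment due to disease progression will not constitute a DLT". The synopsis has the same replacement rule and gives its purpose as evaluating tolerability at that dose level.

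**Replacement afterwards.** Section 5.7 says of patients "who withdraw from the study in the phase II portion of the trial will not be replaced". Section 10.7, naming no phase, says: "Patients who fail to complete treatment for reasons other than adverse event or unacceptable toxicity may be replaced".

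**Denominator.** Section 6.1.2 uses all eligible patients given any treatment who belong to the phase II assessment. Section 6.3 divides by per protocol patients, a set that is not defined. Section 7.1 declares only patients who received no protocol therapy non-evaluable for response.

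**The concern.** Replacing a patient who leaves in cycle 1 suits an assessment of DLTs. It does not suit a response rate. Response is judged after 4 cycles, and Appendix B requires two consecutive assessments for every response category, so a patient who leaves in cycle 1 can hardly be a responder. If such patients drop out of the six while the 23 are not replaced, part of the primary-endpoint sample has been selected on outcome. The cut-offs of 9 and 12 assume 29 patients drawn alike.

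The text leaves two readings, and neither fits the rule. If replaced patients are dropped, the ORR is biased upward. If they are kept in addition to the six, the total passes 29 and the cut-offs were not computed for it. Section 10.7 adds a larger exposure, because read literally it would allow the same selection among phase II patients. What is at stake is the chance of calling an ineffective regimen promising.

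**Working it through.** **Inputs.** From 6.1.2: p0 = 0.25, p1 = 0.50, N = 29 = 6 + 23, promising at 12 or more, not promising at 9 or fewer. The share d of phase I entrants replaced is not in the documents, so it is an assumption, shown over 0 to 30%. Every replaced patient is taken as a non-responder, which is the worst case.

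**1. The plan's own figures.** With X ~ Bin(29, p):

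- type I error = P(X ≥ 12 | 0.25) = 0.0390 (stated 4%)
- eta = P(X ≤ 9 | 0.25) = 0.8337 (stated 0.83)
- pi = P(X ≥ 12 | 0.50) = 0.8675 (stated 0.87)
- type II error = P(X ≤ 9 | 0.50) = 0.0307 (stated 3%)

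All four reproduce after rounding.

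**2. Replaced patients dropped, phase I six only.** Among those retained, the response probability under the null is q = 0.25/(1 − d). Then X = Bin(6, q) + Bin(23, 0.25), expected ORR = (6q + 23 × 0.25)/29, and expected number replaced = 6d/(1 − d). For d = 10%: q = 0.25/0.90 = 0.2778, and expected ORR = (1.667 + 5.75)/29 = 25.6%.

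| d (assumed) | q | Expected replaced | Expected ORR | P(X ≥ 12) | P(X ≤ 9) |
|---|---|---|---|---|---|
| 0 | 0.2500 | 0 | 25.0% | 0.0390 | 0.8337 |
| 5% | 0.2632 | 0.3 | 25.3% | 0.0421 | 0.8248 |
| 10% | 0.2778 | 0.7 | 25.6% | 0.0458 | 0.8146 |
| 15% | 0.2941 | 1.1 | 25.9% | 0.0501 | 0.8030 |
| 20% | 0.3125 | 1.5 | 26.3% | 0.0552 | 0.7895 |
| 30% | 0.3571 | 2.6 | 27.2% | 0.0691 | 0.7550 |

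The type I error passes 0.040 at d = 1.6%, 0.045 at 9.0% and 0.050 at 14.9%.

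**3. Section 10.7 applied to all 29.** X ~ Bin(29, q) gives P(X ≥ 12) = 0.056, 0.080 and 0.164 at d = 5%, 10% and 20%.

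**4. Replaced patients kept on top of 29.** As a plain binomial sample with one extra patient, at least 12 of 30 gives type I error 0.0507 and power 0.900; at least 13 of 30 gives 0.0216 and 0.819. With two extra, at least 12 of 31 gives 0.0644. Adding non-responders to the denominator alone does not help either: the responder count is unchanged, so a fixed cut-off of 12 is met exactly as often as in step 2.

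**5. Every treated patient counted, total held at 29.** Each of the 29 then has response probability p0, however many of them entered in phase I, so X ~ Bin(29, 0.25) again: type I error 0.0390 and power 0.8675.

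The model covers replacement only. It does not cover choice of the MTD by DLT count, or an MTD cohort with fewer than six patients.

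**The case against.** The strongest reply is that the documents never remove a replaced patient from the response analysis. Section 6.1.2 counts treated patients, Section 7.1 makes only untreated patients non-evaluable, and Sections 5 and 6.1.2 speak of six patients treated at the MTD, not six who completed cycle 1. The synopsis ties replacement to tolerability. This stands: exclusion is an inference from the fixed six and the fixed 29 evaluable. But the keep-them reading still exceeds 29, and 6.3 gives a different, undefined denominator.

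A reader might infer that early progressors and withdrawals in general are removed. The text does not support that. The phase I rule covers only non-toxicity exits before the end of cycle 1. Appendix B requires two consecutive assessments for progression, with M-protein measured every 4 weeks, so confirmed progression inside cycle 1 is probably uncommon. Later exits are not replaced under that rule.

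A reader might also infer that the stated 4% is wrong. It is the correct figure for the rule as written, and the effect through the six alone is small.

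Finally, 5.7 is mandatory and specific to phase II, while 10.7 is general and permissive. Treatment under 4.4 is open-ended, so failing to complete it could describe a responder who withdraws late. The step 3 figures are therefore an upper bound, not an expectation. The contradiction between the two sections remains.

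**Conclusion.** The concern holds as a conflict in the plan that leaves the type I error unassured. It is not a demonstrated bias or a failed error rate. If replaced patients are dropped and are non-responders, the bias can only be upward. Through the phase I six alone it is modest: 0.3 to 1.3 percentage points of ORR and a type I error of 4.2% to 5.5% for an assumed 5% to 20% replaced, above 5% only from about 15%. The worst case, 5.6% to 16.4% over the same range, needs 10.7 to override 5.7 for all 29 patients and every replaced patient to be a non-responder. If replaced patients are instead kept on top of 29, even one takes the rule to at least 12 of 30, with a type I error of 5.1%. All of these sizes except the last rest on drop-out rates that the documents do not give.

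**What to change.** 1. In 6.1.2, define the response set as every eligible patient given any study drug at the MTD level, including phase I patients replaced for DLT evaluation. Count unassessed patients as non-responders.
2. Set new phase II accrual to 29 minus the number already treated at the MTD level. The synopsis already gives 23 as a maximum, so a smaller number fits.
3. In 6.3, replace the per protocol denominator with that of 6.1.2.
4. Make 10.7 agree with 5.7, so that phase II patients are not replaced for the response analysis. Replacement for DLT evaluation in phase I can stay as it is.

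This keeps the cut-offs of 9 and 12 and restores type I error 0.039 and power 0.868. It costs protocol and SAP wording and no extra patients. The downside is that the observed ORR may be slightly lower. Showing the phase II-only ORR beside the pooled one is optional.

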5.1 CT-011

5.1.1 Schedule

Table 5-1: Treatment Regimen During Phase I Study: 28 day Cycle

	CT-011- mg/kg day 3
Cohort -1	1.5
Cohort -2	1.5
Cohort 1	1.5
Cohort 2	3
Cohort 3	3
Cohort 4	6

	Lenalidomide- mg Days 1-21
Cohort -1	10
Cohort -2	5
Cohort 1	15
Cohort 2	15
Cohort 3	25
Cohort 4	25

CT-011 is an investigational agent supplied by Medivation, Inc., It is supplied for this protocol for clinical trial use only and it is not commercially available.

5.1.2 Premedication

All patients will receive pain relief medication (Tylenol 650mg or Ibuprofen 800mg or related medication), and an antihistamine (H1 blocker; 25-50mg diphenhydramine hydrochloride administered I.V.). In cases where patients cannot tolerate diphenhydramine hydrochloride, or cases where this medication is not available at the site's pharmacy, an alternative would be to use one of the following as anti-histamine: promethazine at 25mg I.V. administered 20-50 minutes prior to CT-011 dose, chlorpheniramine administered at 10mg I.V 20-50 minutes prior to CT-011 dose, oral chlorpheniramine taken 2 hours prior to CT-011 dose or oral diphenhydramine taken 2 hours prior to CT-011 dose. Anti-histamines given I.V. should be administered as slow IV (NOT as "push"). H2 blockers may be given in addition to H1 at the investigator's discretion but cannot substitute for an H1 anti-histamine. Patients who develop severe infusion reaction requiring intubation will be taken off study.

5.1.3 Route and Method of Administration

CT-011 will be administered intravenously on day 3 of a 28 day cycle.

CT-011 is to be administered intravenously using a peripheral line or a central device if such has been inserted. Patients will be dosed on a mg/kg basis.

The first time CT-011 is to be administered intravenously at a dose of 1.5/3.0/6.0mg/kg delivered over approximately 2 hours as follows:

1. Initial rate of infusion is 50 mL/hr for 30 minutes; If no symptoms related to infusion appear:
2. Increased rate to 100 mL/hr; for 30 minutes; If no symptoms appear:
3. Increased rate to 150 mL/hr for 30 minutes; If no symptoms appear:
4. Increase rate to 200 mL/hr for 30 minutes;

In the event that Grade 3 or higher infusion-related toxicity occurs during infusion, administration of CT-011 should be stopped immediately. Administration of CT-011 could be resumed only after the toxicity has resolved using the slowest rate of infusion (50mL/hr). Once the infusion is resumed, vital signs will be checked every 15 minutes for the first hour, then every 30 minutes till the end of the infusion and then one hour from end of infusion.

If no drug related or infusion related adverse events occur during the first administration, further CT-011 administrations could be delivered over approximately 1:15 hours at a rate of 200mL/hr. Subsequent administrations should be made as scheduled in the absence of Grade 3 or higher adverse events or disease progression.

The maximal administration rate is approximately 250 mg/hr. The total dose administered and the dosing rate will be documented in the patient's medical records.

To ensure complete delivery of CT-011, the IV infusion line must be flushed with 0.9% sodium chloride. The following are two recommended methods for flushing the CT-011 IV infusion line:

- 1) When the CT-011 infusion is complete, add an additional 50mL of 0.9% sodium chloride for

injection to the CT-011 infusion bag. Continue the infusion until a volume equal to that of the volume contained in the tubing has been administered.

- 2) Replace the empty CT-011 infusion bag with a 50mL bag of 0.9% sodium chloride for injection and infuse a volume equal to the volume contained in the tubing. Please note: the flush is not included in the total recommended infusion times.

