Preparation of CT-011 For Administration: The solution will be prepared by a pharmacist, the Investigator, or a study nurse. Appropriate aseptic techniques should be used. Prior to infusion the vial(s) must be thawed at room temperature for approximately 1 hour; the vial(s) should be swirled gently to make sure that the solution is clear, colorless, and transparent. **DO NOT SHAKE!** Effort must be made so that once thawed; the drug will be diluted immediately into an infusion bag and administered to the patient as soon as possible (see Section 8.3 for drug product storage conditions). Each vial contains **approximately** 20 mg/mL CT-011. While most lots will be provided at this concentration, note that current specifications allow for a concentration range of 19mg/ml to 21mg/ml. Determine the total amount of CT-011 required based on the drug handling sheet provided keeping in mind that maximal total dose allowed is 600mg per patient

The appropriate amount of CT-011 solution should be withdrawn from the vial(s) and added to an infusion bag containing 250 mL of 0.9% sodium chloride solution, USP. The bag will be identified with the patient number. The bag should then be gently inverted to mix the solution in order to avoid foaming. Parenteral solutions should be inspected visually for particulates and discoloration prior to administration. Once the infusion is prepared, it should be administered immediately.

Method of Administration: CT-011 will be administered intravenously on day 3 of each 28 day cycle. The drug is diluted into a 250mL saline bag which in the FIRST infusion is administered in a step-wise manner: 50ml/hr for 30min; 100ml/hr for 30min; 150ml/hr for 30 min and 200ml/hr till the end (another ~30min) for an approximate time of 2hrs. If no infusion related AEs occurs the first time, subsequent administrations are at 200mL/hr which will deliver the drug over approximately 1:15hrs. In the event that Grade 3 or higher toxicity occurs during infusion, administration of CT-011 should be stopped immediately. Administration of CT-011 could be resumed only after the toxicity has resolved using the slowest rate of infusion (50mL/hr). Vital signs will be measured prior to infusion and every 15 minutes for the first hour, then every 30 minutes for an additional hour, and then once an hour until the end of infusion.

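### At 6 mg/kg the scheduled 200 mL/hr exceeds the stated maximum of about 250 mg/hr in patients above about 52-56 kg, and no text says which limit governs

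*Combined protocol and SAP*

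**What the plan says.** Section 5.1.3 covers doses of 1.5, 3.0 and 6.0 mg/kg with a single scheme. The first infusion is "delivered over approximately 2 hours as follows": 50, 100 and 150 mL/hr for 30 minutes each, every increase depending on the absence of symptoms, and then "Increase rate to 200 mL/hr for 30 minutes". For later cycles the section says that "further CT-011 administrations could be delivered over approximately 1:15 hours at a rate of 200mL/hr". It makes this depend on tolerance of the first dose: "If no drug related or infusion related adverse events occur during the first administration". Shortly afterwards it sets a limit in different units: "The maximal administration rate is approximately 250 mg/hr".

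Section 9.1 fixes the volume. The drug solution, at about 20 mg/mL, is "added to an infusion bag containing 250 mL of 0.9% sodium chloride solution, USP". On the amount of drug it says "Determine the total amount of CT-011 required based on the drug handling sheet provided", and it notes that the "maximal total dose allowed is 600mg per patient".

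The method of administration in 9.1 and the Study Design entry of the synopsis repeat the mL/hr scheme. Both run the last step of the first infusion until the bag is finished. Both state, without the permissive verb of 5.1.3, that later infusions run at 200 mL/hr in about 1:15 h if the first caused no infusion-related event. Neither mentions the mg/hr maximum.

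**The concern.** A pump set in mL/hr delivers a mass rate that rises with the dose in the bag. With a fixed bag volume, one mL/hr scheme for a fourfold range of doses cannot hold a fixed mg/hr limit unless that limit lies above the top dose. Here it does not, and no text adjusts the pump rate for dose or weight. The only rate reduction described is the restart at 50 mL/hr after a Grade 3 or higher toxicity.

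The dose level affected is a planned one. Cohort 4 gives 6 mg/kg, section 4.3 adds 6 mg/kg cohorts with 15 or 10 mg lenalidomide, and phase II would use it if it is carried forward. Staff working from 9.1 would not see the maximum, while staff working from 5.1.3 might slow the pump. Sites could therefore infuse the same dose at different rates, and a recorded rate could count as a deviation under one section and as compliant under another.

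**Working it through.** **Inputs.** Doses and pump rates: 5.1.3. Bag volume, vial concentration (about 20 mg/mL) and 600 mg cap: 9.1. I read the cap as applying to each infusion. The documents give no body weights, so the weights below are illustrative.

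**Symbols.** D = dose in mg; r = pump rate in mL/hr; V = volume in the bag. Case A ignores the drug volume, V = 250 mL. Case B adds it, V = 250 + D/20 mL.

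**The plan's own times reproduce under case A.** First infusion: 0.5 × (50 + 100 + 150 + 200) = 250 mL in 2 h. Later infusions: 250/200 = 1.25 h = 1:15 h.

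**Dose at which 200 mL/hr reaches 250 mg/hr.** Mass rate = D × r / V.
- A: 200D/250 = 250, so D = 312.5 mg.
- B: 200D = 250 × (250 + D/20), so 187.5D = 62,500 and D = 333.3 mg.
- At 6 mg/kg: 312.5/6 = 52.1 kg and 333.3/6 = 55.6 kg.
- At 3 mg/kg: 104.2 kg and 111.1 kg. At 1.5 mg/kg: 208 kg and 222 kg.

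**Mass rate at 200 mL/hr, 6 mg/kg**

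| Weight | D (mg) | B (mg/hr) | A (mg/hr) | Over 250 |
|---|---|---|---|---|
| 60 kg | 360 | 360 × 200/268 = 269 | 288 | 7-15% |
| 70 kg | 420 | 420 × 200/271 = 310 | 336 | 24-34% |
| 80 kg | 480 | 480 × 200/274 = 350 | 384 | 40-54% |
| 100 kg (cap) | 600 | 600 × 200/280 = 429 | 480 | 71-92% |

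For comparison, a 70 kg patient at 3 mg/kg (210 mg) receives 161-168 mg/hr, so there is no conflict.

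**First infusion.** The 150 mL/hr step passes 250 mg/hr only above 416.7 mg (A) or 454.5 mg (B), that is 69.4 or 75.8 kg at 6 mg/kg. The 100 mL/hr step would need 625 mg or more, above the cap. The average rate is D / (1.5 + (V − 150)/200): at 420 mg, 420/2 = 210 (A) or 420/2.105 = 200 mg/hr (B). It reaches 250 mg/hr at 500 mg (83.3 kg) or 533.3 mg (88.9 kg). The excess therefore lies in the late steps.

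**Later infusions.** These run at 200 mL/hr from start to finish, so any excess lasts throughout.

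**If the maximum governs.** The highest pump rate is 250V/D: 149-161 mL/hr at 420 mg and 104-117 mL/hr at 600 mg. The shortest later infusion is D/250 h:
- 420 mg: 1.68 h = 1:41 h, against 75 min (A) or 271/200 h = 81.3 min (B), so 20-26 min longer.
- 600 mg: 2.4 h = 2:24 h, against 75 min or 84 min, so 60-69 min longer.

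A first infusion with the same cap, run until empty:
- 420 mg: 130.6 min (A) or 135.0 min (B), against 120 or 126.3, so 9-11 min longer.
- 600 mg: 160.8 or 165.4 min, against 120 or 129, so 36-41 min longer.

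**The case against.** A maximum ordinarily limits a schedule, and in 5.1.3 it follows closely on a sentence that permits 200 mL/hr but does not require it. A reader might infer that staff are bound to break one instruction or the other. For later infusions 5.1.3 does not support that: a slower pump breaks nothing there. What stands is the conflict with the firmer wording of 9.1 and the synopsis, and with the late fixed-rate steps of the first infusion.

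The limit is only approximate. Assuming a 10% tolerance (275 mg/hr), the crossing point moves to 275 × 250/200 = 343.8 mg (57.3 kg) in case A, or 68,750/186.25 = 369.1 mg (61.5 kg) in case B. So 52-56 kg is a soft line, and the excess at 60 kg can be argued away. The 24-34% excess at 70 kg cannot.

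The figure may be a unit slip. Every other administration rate in 5.1.3, 9.1 and the synopsis is in mL/hr, and at 250 mL/hr nothing would be exceeded. The documents cannot settle this, but a wrong unit on a maximum rate needs correcting too. Section 9.1 also refers to a drug handling sheet that is not in the documents. It is tied there to the amount of drug, and whether it also covers rate is unknown.

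A reader might infer harm from the melanoma study in 1.4.3, where nearly all listed infusion reactions were at 6 mg/kg. That table gives no infusion rates, and the single-agent phase 1 study, which went up to 6 mg/kg, reported no infusion reactions (1.4.2, 5.1.4). Premedication, symptom-gated steps and a stop rule are in place, and the dosing rate must be recorded.

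A reader might also infer that slowing the pump would leave drug undelivered, because 5.1.3 gives the last step 30 minutes. But 9.1 and the synopsis run that step to the end of the bag, and 5.1.3 requires a flush so that delivery is complete.

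**Conclusion.** The inconsistency is real and is in practice confined to 6 mg/kg. There the scheduled 200 mL/hr passes the stated maximum above about 52-56 kg, and clearly so from about 70 kg: 310-336 mg/hr, rising to 429-480 mg/hr at 600 mg. At 3 mg/kg only patients above about 104-111 kg are affected.

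The result rests on the 250 mL bag, a concentration of about 20 mg/mL and the 600 mg cap read as per infusion. How many patients would be affected is unknown, because no weights are given. The documents do not show which of the two figures is wrong.

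Cycle 1, the only window for dose-limiting toxicity, contains just the first infusion, so the excess there is limited to the late steps. In later cycles it lasts the whole infusion, but only for patients who tolerated the first one well enough to move to 200 mL/hr. No endpoint, sample size or error rate changes. This is a minor to should-fix text correction; confidence is high on the mismatch and does not extend to any clinical consequence.

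**What to change.** Before the first 6 mg/kg dose, the sponsor confirms whether the 250 mg/hr maximum applies.

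If it does, add the same sentence to 5.1.3, 9.1 and the synopsis:

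> The rate must not exceed 250 mg/hr; where the scheduled mL/hr would exceed this, reduce the pump rate to 250 × bag volume (mL) / dose (mg) and run until the bag is empty.

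State the 2 h and 1:15 h times as minimums, and note that a later infusion takes at least dose/250 h (for example 1:41 h at 420 mg and 2:24 h at 600 mg).

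If 250 mg/hr is a unit error, correct or delete it and leave the schedule alone.

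The cost is one confirmation and wording in up to three places, with no extra patients or data. If the maximum governs, chair time is the downside: later infusions run about 20-26 minutes longer at 70 kg and 60-69 minutes longer at 600 mg, and first infusions about 9-11 and 36-41 minutes longer. The 2-hour room-temperature limit in 9.1 applies before the infusion starts, so it is not breached. The end-of-infusion and 1-hour pharmacokinetic samples in 8.1 are timed from the end of infusion and move with it.
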